9.4 Data Sources

Data from 2 existing international registries covering countries with expected access to exa-cel will be used:

- EBMT Registry
- CIBMTR Registry

Both the EBMT and CIBMTR registries have primary data collection capabilities for supporting pharmacoepidemiologic research studies. Primary and secondary data collected via these 2 registries will allow for the characterization of longitudinal patterns in a broad range of safety and effectiveness outcomes within cohorts of exa-cel-treated patients and allo-HSCT comparator patients in both Europe and the US. Each registry has data consistency checking and an auditing mechanism to verify the validity of the data reported (Sections 9.6 and 9.8). Each registry also has Committees / Working Parties that oversee the management and scientific integrity of registry operations (see Annex 2 and Annex 3).

Standard registry forms and customized study-specific reporting forms jointly developed by sponsor and registry operators will allow data to be collected on outcomes and other key variables essential to meet the objectives of the study. Data will be collected at standard timepoints following receipt of therapy for the first post-transplant year, and annually thereafter. The data collection responsibilities of the participating transplant centers, including the efforts to ensure long-term patient follow-up as well as SAE reporting responsibilities, will be outlined in the site agreements, as applicable.

Existing standard registry-specific data collection forms to be used for this study can be found in Annex 4.

9.4.1 EBMT

The EBMT is a non-profit organization registered in the Netherlands, first established in 1974. The EBMT registry holds data on patients given a HSCT or cellular therapy infusion procedure. The registry holds data on more than 680,000 patients that received a transplant procedure as well as data on more than 6,000 patients that received a chimeric antigen receptor T-cell therapy. The registry receives data from approximately 80% of European transplant centers and is the principal source of data in the field for clinical research for retrospective clinical studies,

epidemiological trends and feasibility studies for prospective clinical studies. In more recent years, the EBMT Registry has been used for regulatory purposes and represents a valuable research tool for future long-term studies of outcomes among recipients of gene therapies requiring an autologous HSCT procedure.

The EBMT full membership requires clinical transplant centers to commit to submit a minimum set of data on all patients treated in their center on an annual basis. The duty is to report all consecutive HSCT and other cellular therapies and follow-up data.

In August 2023, EBMT moved to a new platform for data collection called EBMT Registry (Section 9.6.1). This innovative platform replaces ProMISe and Castor, streamlining data management practices for a more cohesive user experience.

EBMT standard data collection forms can be divided into the Core Dataset Forms and the Extended Dataset Forms:

- 1. **Core Dataset Forms**: These forms collect the minimum essential data that must be provided by all member centers for their consenting patients.
- 2. Extended Dataset Forms: These forms collect additional information that can be provided by centers to keep more details on a patient's medical history, or if the EBMT working party requests this information for a specific study. It includes items with more detailed questions that are relevant to most studies conducted by EBMT Working Parties. Data from the extended dataset is collected through a number of additional forms and can only be entered in addition to the core dataset.

In addition, study-specific forms can be developed and implemented in close collaboration between the sponsors and EBMT to meet the needs of individual research studies and will contain those fields specific for a study that are not present in existing forms.

9.4.2 CIBMTR

The CIBMTR[®] is a non-profit research collaboration between the National Marrow Donor Program (NMDP)[®] / Be The Match[®] and the Medical College of Wisconsin in the US. The CIBMTR is now in the seventeenth year of a robust, collaborative affiliation and outcomes-focused research endeavor. The CIBMTR Coordinating Center is committed to supporting the highest level of clinical and health services research. The CIBMTR collaborates with the global scientific community to advance HSCT and other cellular therapy worldwide to increase survival and enrich quality of life for patients. Their prospective and observational research is accomplished through scientific and statistical expertise, a large network of transplant centers, and a clinical database of more than 600,000 patients.¹⁴ CIBMTR has been successfully used for hundreds of clinical research studies positively impacting both clinical practice and transplant patients; this includes studies conducted as commitments to regulatory authorities.

CIBMTR standard data collection forms include:

• **Transplant Essential Data (TED) Forms:** These forms collect the core, transplant essential data. TED form completion is mandatory for allogeneic transplants occurring (or using donor material from) in the US; complete reporting, including autologous transplant activity, is requested for all centers that report allogeneic activity. Essential data forms include information on the indication for the procedure (including hemoglobinopathy), information on patient demographics, health status, and common comorbidities prior to transplant;

transplant type, preparative regimen, and recovery; plus, post-transplant secondary malignancies, vital status, and cause of death.

• **Comprehensive Report Forms (CRF):** The CRF-level data capture additional patient, disease, and treatment-related data. These are more extensive forms, completed regularly by a smaller fraction of the centers that have agreed to provide CRF-level data. The CIBMTR SCD and thalassemia pre-infusion data and SCD post-infusion data CRFs collect targeted information on disease diagnosis, disease-related organ damage accrued prior to the transplant, disease-related medication history, and disease status following transplant. Centers will collect CRF-level data for all enrolled study participants.

In addition, study-specific forms can be developed and implemented in close collaboration between the sponsors and CIBMTR to meet the needs of individual research studies and will contain those fields specific for a study that are not present in existing forms.

9.5 Study Size

Exa-cel is an advanced therapeutic medicinal product targeted for individuals with 1 or more severe manifestations of rare hematologic disorders. HSCT for SCD and TDT is a rare procedure, with allogeneic transplants for SCD and TDT representing only a small fraction of the total annual HSCT volume managed by transplant centers. In 2019, hemoglobinopathies were only 1.4% of the HSCT volume reported to the EBMT¹⁵, and 1.1% of the reported volume in the US.^{16, 17} The average number of transplants performed historically (2016 through 2019) in Germany, France, Italy, UK, and US for patients with SCD and TDT who are 12 years of age and older without a matched donor (equivalent to the population indicated for exa-cel) is approximately 70 patients per year (CIBMTR data on file, EBMT data on file).¹⁶ It is expected that exa-cel will be available to only small numbers of patients in routine clinical practice.

As such, exa-cel enrollment targets include a minimum of 100 treated patients with TDT and 100 treated patients with SCD for a minimum of 200 exa-cel treated patients across all regions included in the study. It is expected that the enrollment period will be up to approximately 3 years, though may be extended to up to 5 years enrollment if the minimum sample size is not reached within 3 years.

It is anticipated that there will be an approximately equal number of allo-HSCT comparator patients enrolled. While eligibility for the Allo-HSCT Cohorts will be limited to patients aged 12 years and older, it will not be limited by donor type and may include patients from the larger pool of individuals receiving matched, mismatched or haploidentical donor transplants (see Section 9.1.2 for full inclusion / exclusion criteria).

Exa-cel uptake under real-world conditions is ultimately unknown and may be impacted by factors such as access and reimbursement, transplant center capacity to treat patients with newly available gene therapies, advances in allogeneic transplantation such as haploidentical transplant, potential availability of other gene or oral therapy products, and other unforeseen factors. Nevertheless, it is anticipated that approximately 1/3 of the final enrolled sample will be from European centers.

9.6 Data Management

Data management is maintained at each registry according to their internal processes.

9.6.1 EBMT

In August 2023, EBMT moved to a new electronic data capture platform for data collection which replaces ProMISe and Castor platforms. The EBMT Registry is a flexible data entry web application, connected to a fast and responsive live application database, enabling users to enter and retrieve data. The application database is then connected to the analytical database where all the data is restructured and organized according to the Observational Medical Outcomes Partnership (OMOP) Common Data Model (CDM) (for more details on OMOP CDM please refer to https://ohdsi.github.io/CommonDataModel/).

To ensure the data entered into the database is complete, correct, accurate, allowable, valid, and consistent, the following data quality edit checks will be implemented where applicable:

- EBMT Registry system-generated edit checks
- Automated (SPSS/R programmed) edit checks
- Manual edit checks by EBMT Statisticians, data managers, clinical study coordinators, monitors, or any applicable user
- Medical review by the EBMT medical officer
- Study specific data retrieval is a verified process caried out by the qualified data managers and enabled by qualified information technology specialists. After data are extracted for a study-specific need, the datasets undergo an analyses dataset preparation process, which includes
 - data verification by qualified and experienced data managers and monitors at the EBMT Clinical Study Unit; and
 - study data file preparation: analyses dataset, by qualified and experienced statisticians and medical experts at the EBMT

The study data file preparation takes place in order to enable data analytics on the EBMT Registry collected data, study statistical analyses, site management, and study management.

9.6.2 CIBMTR

The FormsNetTM application is a secure clinical research management system for electronic submission of outcome data to the CIBMTR, in compliance with the Stem Cell Therapeutic Outcomes Database. Training is available through the CIBMTR.

Data extraction from the CIBMTR database and data transformation is performed by Master-level biostatisticians with relevant expertise. Data cleaning is performed in conjunction with the scientific director, who has in-depth knowledge of data collection by the CIBMTR and clinical expertise in transplantation and cellular therapies. The CIBMTR Data Operations Department assists with any queries to centers for clarifying data during the data cleaning process. The CIBMTR Master-level biostatisticians, in collaboration with Doctorate-level biostatisticians, perform the analyses. The CIBMTR has a unique partnership and close collaboration with the Division of Biostatistics at the Medical College of Wisconsin that includes PhD-level statistical support for studies.

9.7 Data Analysis

All analyses for this study will be performed by the respective statistical / programming teams using SAS, SPSS, R, or equivalent statistical software. All outcome variables specified in Sections 9.3.3 through 9.3.5 will be evaluated for both the exa-cel and allogeneic HSCT cohorts, including the TDT Exa-cel, TDT Allo-HSCT, SCD Exa-cel and SCD Allo-HSCT Cohorts. Patient-level data (pseudonymized) will additionally be available, for both exa-cel and allo-HSCT cohort participants, with patient consent / assent.

To meet the study objectives, data will be analyzed separately for each registry and each cohort at pre-specified timepoints over the study duration. Each interim report will include separate analyses of the data collected by each registry and will provide a descriptive comparison of the EBMT and CIBMTR patient populations in terms of (i) demographic and clinical characteristics, (ii) treatment(s) received, and (iii) outcomes. In addition to the separate analyses within each registry, pooled analyses of key safety outcomes (Section 9.3.3) will be performed at prespecified timepoints (after a 5-, 10-, and 15-year duration of follow-up is accrued for all enrolled patients), unless substantial heterogeneity is observed between the two registries. Any potential issues precluding variable harmonization across the two registries will be discussed in the analysis reports. Pooled analysis of additional outcomes may be performed if feasible and warranted. The results of the interim and final analyses will be presented in interim and final study reports.

Descriptive statistics will be presented for all study outcomes:

- **Continuous variables** will be summarized using the following descriptive summary statistics, where appropriate: the number of observations, mean, standard deviation, 95% CI, median, minimum value, maximum value, and 25th and 75th percentile values.
- **Categorical variables** will be summarized using counts, percentages, and 95% CIs, as appropriate.

Crude risks, crude relative risks with 95% CI, and odds ratios with 95% CI will be calculated for outcomes, as appropriate. Cumulative incidence, treating death as a competing risk, will be calculated and presented for select safety outcomes. Overall survival curves will be produced.

Long-term safety and effectiveness outcomes among exa-cel recipients will be evaluated for the TDT Exa-cel and SCD Exa-cel Cohorts within each registry separately. Comparisons of the post-transplant period to pre-transplant period will be performed, as appropriate.

Between cohort results, comparing the Exa-cel Cohorts to their appropriate Allo-HSCT Cohort, will also be evaluated within each registry separately.

Subgroup analyses will be performed by age group, genotype, and/or other patient characteristics such as baseline disease severity, as appropriate. Subgroup analyses by country of transplant may be performed if sufficient patient counts are available to preserve patient anonymity. Additional ad-hoc statistical analyses may be implemented, as needed – this may include modeling to adjust for differences in cohort characteristics in between-cohort analyses and/or time to event analyses for select outcomes. A discussion of potential confounders associated with the key safety outcomes among patients with hematologic diseases is provided in Section 9.9.2.

Findings will be discussed in the context of available published literature on the natural history of TDT and SCD under the medical standard of care, as appropriate.

Further details will be provided within the statistical analysis plan.

9.7.1 Definition of Study Periods

For safety and effectiveness outcome analyses within the Exa-cel and Allo-HSCT Cohorts the pre-transplant and post-transplant periods will be defined as described below and illustrated in Figure 2:

- **Day 0 (transplant date)** is defined as the day of exa-cel product or allogeneic donor cell infusion, depending on cohort, as reported to the registries.
- **The pre-transplant / baseline period** will be broadly defined as the period prior to Day 0, with the length of the period varying depending on the study measures being evaluated:
 - For the *primary disease severity* measures (see Section 9.3.4 Effectiveness Outcome Variables) and *disease-related therapies* (see Section 9.3.5), the baseline period will be defined as 1 year prior to initiation of the conditioning regimen.
 - For *laboratory measures*, baseline will be defined as the non-missing measure most proximal, but prior to treatment initiation. This includes effectiveness measures such as total Hb, Hb fractionation (e.g., % HbS for SCD) and serum ferritin (see Section 9.3.4) as well other laboratory measures (see Section 9.3.5).
 - For pre-transplant *disease-related end-organ damage or dysfunction* (see Section 9.3.5) baseline will be defined as any time prior to the transplant.
 - Other variables such as patient demographics, pre-transplant height, weight and health status will be as reported at the most recent time point prior to transplant.
- The post-transplant period will continue for up to 15 years after the final enrolled patient's Day 0. For each patient, Year 1 will include events, new diagnoses or findings, and/or therapies initiated (or continued) within the first 365 days after Day 0; Year 2 will include the same occurring from patient day 366 to day 730, etc. Year 1 will further include the following time intervals based on existing transplant registry reporting: Day 0 to Day 100, Day 100 to 6 months, and 6-month to 1-year reporting. All patients, both exa-cel treated or comparator, will be followed for up to 15 years. Patients will be censored to last reported timepoint only after 2 years of loss to follow-up.

Figure 2 Study Periods

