7 RATIONALE AND BACKGROUND

7.1 Background

 β -thalassemia is an inherited autosomal recessive blood disease characterized by reduced hemoglobin (Hb) production. Caused by mutations in the *HBB* gene, disease severity varies across a spectrum from intermedia to thalassemia major. β -thalassemia major, also called transfusion-dependent β -thalassemia (TDT), is fatal within the first few years after diagnosis if left untreated. Symptoms of TDT appear within the first 2 years of life and include severe anemia, splenomegaly, bone marrow expansion, failure to thrive and ultimately, death.

Sickle cell disease (SCD) is caused by a single nucleotide substitution in which a valine replaces a glutamic acid at position 6 of the β -globin chain leading to an abnormal or sickle cell Hb (HbS). HbS polymerizes in the deoxygenated state producing abnormal, sickle shaped red blood cells (RBCs) with limited flexibility and lifespan. These rigid cells are responsible for painful vaso-occlusive crisis (VOC), chronic anemia, inflammation, stroke, organ failure, and early mortality.

Exagamglogene autotemcel (exa-cel) is a cellular product consisting of autologous CD34⁺ human hematopoietic stem and progenitor cells modified by CRISPR-Cas9-mediated gene editing of the erythroid enhancer region of the *BCL11A* gene located on chromosome 2. *BCL11A* is a transcriptional silencer of γ -globin gene expression and hence a negative modulator of fetal Hb (HbF) production. Shortly before birth, *BCL11A* is turned on and there is a switch from HbF to adult Hb (HbA), which is made up of 2 α -globin chains and 2 β -globin chains. The switch from HbF to HbA is mediated by a transcriptional switch from γ -globin to β -globin expression within the β -globin gene cluster located on chromosome 11. CRISPR-Cas9 is "clustered regularly interspaced short palindromic repeats and CRISPR-associated 9 nuclease". Cas9 is an enzyme that uses CRISPR guide RNA (gRNA) sequences to cleave a specific genomic locus that is complementary to the CRISPR gRNA. The goal of this genetic modification is to reactivate the expression of γ -globin messenger RNA in erythroid precursors, which in turn leads to an increase in HbF protein levels in adult erythroid cells.

Exa-cel is intended to treat disorders caused by genetic defects that affect the production or function of Hb molecules (β -thalassemia, SCD).

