9.3.4 Effectiveness Outcome Variables

Variables described in this section are to: (i) characterize disease status at baseline and (ii) allow direct and indirect assessment of the effectiveness and durability of the transplant. Characterization of the type and number of transfusions (among TDT and SCD patients) and/or severe VOC events (SCD patients only) pre- and post-transplant allows determination of whether overt disease symptomatology has been corrected with the transplant. Hb measures, including total Hb concentration as well as Hb fractionation (e.g., % HbS among patients with SCD), allows tracking of graft uptake and function at a more cellular level than the symptomatic measures. Iron concentration and iron overload management are secondary measures of graft function, as cessation of primary symptomology (transfusion dependence) should lead to measurable decreases in iron burden and a reduced need for iron overload therapies over time. Measures of organ dysfunction at baseline and over time are also secondary measures of graft function as successful correction of the underlying genetic deficiency is expected to prevent further accumulation of organ damage over time and/or prevent new disease-related organ damage events from occurring. These measures encompass the core effectiveness assessment for the transplant.

The following effectiveness outcomes will be recorded:

- **Primary disease severity measures** will be recorded pre- and post-transplant as summarized in the schedule of data collection presented in Section 9.3.6. Specifically, pre-transplant these events will be quantified for the 1 year (12 months) preceding initiation of the conditioning regimen:
 - RBC transfusion events (TDT and SCD) to be defined as the receipt of RBCs for the purpose of primary disease management (i.e., anemia). Number of RBC transfusions and number of units transfused will be recorded pre- and post-transplant (as available) as summarized in the schedule of data collection. Time from HSCT to most recent transfusion will be recorded.
 - Severe VOC events (SCD only): Number of severe VOC events will be recorded pre- and post-transplant as summarized in the schedule of data collection presented in Section 9.3.6. Time from HSCT to most recent severe VOC event will be recorded.

Severe VOC events will include any/all of the following events:

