9.3.5 Additional Key Variables

Additional key variables encompass general patient characteristics (e.g., demographics and health status), supporting transplant and laboratory measures (e.g., complete blood count [CBC]), and additional transplant-related complications (e.g., infection, bleeding, veno-occlusive liver disease) that may be of importance. The hematopoietic cell transplantation comorbidity index (HCT-CI) captures a wide range of co-existing diseases or organ impairments relevant to HSCT outcomes such as renal or hepatic impairment and prior history of malignancy. These variables may be considered as covariates for subgroup analyses and/or allow to further characterize the post-transplant outcomes.

Additional key variables will be recorded pre- and/or post-transplant as summarized in the schedule of data collection presented in Section 9.3.6 to assess patient demographics and general health status.

• Demographics

- Age at initial disease diagnosis
- Age at transplant
- o Sex
- Race, Ethnicity (US only)
- Country of transplant

- Payor type (US only)
- Health status
 - Performance score (Karnofsky for ages ≥ 16 years or Lansky for ages < 16 years)
 - Hematopoietic cell transplantation comorbidity index (HCT-CI) items¹³
 - Height
 - o Weight
 - Smoking history
- Additional transplant details will be recorded at the time of transplant, as available.
 - Preparative regimen (myeloablative, reduced-intensity, non-myeloablative, unknown)
 - Conditioning agent(s), including dose, start date, as available
 - \circ CD34⁺ cell infused dose, if available
 - Mobilization agent (Exa-cel Cohorts only)
 - Product identification (Exa-cel Cohorts only)
 - Donor type (Allo-HSCT Cohorts only)
 - Donor matching (Allo-HSCT Cohorts only)
 - Cell source (Allo-HSCT Cohorts only)
- **Disease-related therapy** use will be recorded pre- and post-transplant as summarized in the schedule of data collection presented in Section 9.3.6, to be defined as prescription or in-hospital use (i.e., for opioids) of the below agents or interventions at any time in the 1 year prior to HSCT (pre-transplant) or since the prior visit (post-transplant):
 - o Crizanlizumab
 - o Hydroxyurea / Hydroxycarbamide
 - o L-glutamine
 - Luspatercept
 - Narcotics / Opioids (for indication-related pain, only)
 - Non-narcotic and/or nonsteroidal anti-inflammatory drug analgesics (for indication-related pain, only; if available)
 - Voxelotor

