allo-HSCT: allogeneic HSCT; exa-cel: exagamglogene autotemcel; Hb: hemoglobin; HbF: fetal Hb; HSCT: hematopoietic stem cell transplantation; RBC: red blood cell; SCD: sickle cell disease; US: United States; VOC: vaso-occlusive crisis Note: Time to event will be captured for all variables, where specified in Section 9.3.

^a Data on history pre-HSCT will be collected retrospectively at enrollment. This may include: transfusion (TDT and SCD) and/or severe VOC (SCD only) rates in the 1 year prior to preparative regimen initiation, historic diagnoses, pre-transplant therapies in the 1 year prior to HSCT, recent pre-transplant laboratory findings, etc.

^b The non-missing measurement most proximal to the data report date.

^c Exa-cel Cohorts only

^d Allo-HSCT Cohorts only

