9.7.4 Effectiveness Analyses

Effectiveness analysis outcomes will be evaluated for each cohort from each registry for each post-transplant follow-up period. Analyses will be performed overall and in subgroups by patient age group, genotype, and/or other category, as appropriate and if sufficient data are available. Additional analyses may be performed for outcomes deserving further investigation if sufficient data are available. Statistical testing may be performed comparing the frequencies or rates of outcomes from the TDT Exa-cel and TDT Allo-HSCT Cohorts, and the SCD Exa-cel and SCD Allo-HSCT Cohorts, if sufficient data are available.

- For the primary disease severity measures, descriptive statistics for the number of events in the 1 year prior to the preparative regimen initiation and at each of the post-transplant follow-up periods will be reported:
 - Number of RBC transfusion events (TDT and SCD)
 - Number of severe VOC events (SCD only)

Proportions of patients who are RBC transfusion-free, severe VOC-free or severe VOC hospitalization-free (as appropriate) will also be reported at each timepoint of the post-transplant periods.

Time RBC transfusion-free or VOC-free, from Day 0 to the most recent event, will also be summarized.

- **Hb measures** (total Hb, % HbF, % HbS [where relevant]) will be summarized as continuous variables for each timepoint of the post-transplant period, with a 95% CI, among patients with an observation.
- **Iron concentration measures** (serum ferritin, LIC, CIC) will be summarized as continuous variables for each timepoint of the post-transplant period, with a 95% CI, among patients with an observation.

Absolute change from baseline may be calculated for patients with non-missing baseline and post-transplant years.

• New disease-related end-organ damage or dysfunction diagnoses will be summarized for each timepoint of the post-transplant period as the proportion of patients with a new diagnosis (i.e., categorical variables), with a 95% CI.

Cumulative diagnoses over the entire post-HSCT observation period may be reported for select diagnoses.

• Use of iron overload management tools (chelation therapy, phlebotomy) will be summarized for each timepoint of the post-transplant follow-up period as the proportion of patients receiving therapy (i.e., categorical variables).

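### The baseline year for transfusions and severe VOCs ends at conditioning, so in the Exa-cel Cohorts it normally takes in cell-preparation time that the listed data cannot separate out

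*Protocol*

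**What the plan says.** The anchor for disease-severity events is stated consistently:

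- 9.7.1: "the baseline period will be defined as 1 year prior to initiation of the conditioning regimen".
- 9.3.4: "pre-transplant these events will be quantified for the 1 year (12 months) preceding initiation of the conditioning regimen".
- 9.7.4 summarizes "the number of events in the 1 year prior to the preparative regimen initiation", and Table 2 footnote a uses the same anchor for transfusions and VOCs.

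On preparation, 7.1 describes autologous CD34+ cells "modified by CRISPR-Cas9-mediated gene editing of the erythroid enhancer region", and Section 12 refers to stored unedited cells and drug-product retains. Section 9.3.5 lists "Mobilization agent (Exa-cel Cohorts only)" with no date, while for conditioning it lists "Conditioning agent(s), including dose, start date, as available". Table 2 has a baseline row for mobilization and conditioning, also without a mobilization date.

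Two other baselines are anchored differently. For disease-related therapies, 9.7.1 uses the year before conditioning, but 9.3.5 uses the year before HSCT and Table 2 footnote a says "pre-transplant therapies in the 1 year prior to HSCT". For laboratory values, 9.7.1 says "baseline will be defined as the non-missing measure most proximal, but prior to treatment initiation", while Table 2 footnote b takes the value nearest to the date of the data report.

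**The concern.** A pre-treatment year should measure the same kind of time in each group being compared. Here one group's year contains a treatment-preparation phase and the other's contains no mobilization or manufacture. Nothing in the protocol excludes that interval, reports it separately or lists it among the limitations in 9.9.

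The baseline counts are used in three places: the pre-post comparison within the Exa-cel Cohorts (9.1, 9.7), subgroups in which baseline severity is named as an example (9.7), and the exa-cel versus allo-HSCT baseline comparison, where major differences are to be handled by stratification or modelling (9.7.2). A severity measure that covers different care in the two groups could create an imbalance or hide one.

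This is a question of data capture as well as analysis. Baseline history is described as a rate over one year, gathered retrospectively at enrollment. A single 12-month count with no mobilization date cannot be divided later, whatever the SAP prescribes.

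**Working it through.** **Order of events.** Cells must be collected before they are edited, and edited before they are infused. Section 9.1 places conditioning in the immediate peri-transplant period. Mobilization therefore precedes conditioning, and some or all of the mobilization-to-conditioning interval lies in the 12 months that end at conditioning.

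**Inputs.** The window is 12 months (9.3.4, 9.7.1, 9.7.4, Table 2 footnote a). The protocol states no figure on this point, so there is none to reproduce. Two quantities have to be assumed:

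- m, the months of the baseline year after mobilization starts: 2 to 9.
- k, the event rate in those months divided by the rate before them: 0.5 to 3.

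**Step 1: recorded baseline divided by true baseline.**

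M = (12 − m)/12 + (m/12) × k

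Low end, m = 9 and k = 0.5: 3/12 + 9/12 × 0.5 = 0.625. High end, m = 9 and k = 3: 3/12 + 9/12 × 3 = 2.50.

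| m (months) | k = 0.5 | k = 1 | k = 2 | k = 3 |
|---|---|---|---|---|
| 2 | 0.92 | 1.00 | 1.17 | 1.33 |
| 4 | 0.83 | 1.00 | 1.33 | 1.67 |
| 6 | 0.75 | 1.00 | 1.50 | 2.00 |
| 9 | 0.63 | 1.00 | 1.75 | 2.50 |

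With k = 1 there is no distortion for any m. With k unknown, the direction is unknown too.

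**Step 2: relative reduction.** Let r be the post-transplant rate divided by the true baseline rate. The recorded reduction is 1 − r/M.

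| True reduction | r | Recorded at M = 0.625 | Recorded at M = 2.5 |
|---|---|---|---|
| 100% | 0 | 100% | 100% |
| 95% | 0.05 | 92% | 98% |
| 80% | 0.20 | 68% | 92% |
| 50% | 0.50 | 20% | 80% |

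If events nearly disappear after transplant, the relative reduction hardly moves.

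**Step 3: absolute change.** Recorded divided by true change is (M − r)/(1 − r). With r = 0 this equals M, so the absolute fall is recorded at 0.63 to 2.50 times its true size even when the relative reduction is unaffected.

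**Step 4: between-cohort baseline.** If the true baseline rates were equal and the allo-HSCT year unaffected, the recorded exa-cel/allo-HSCT ratio would be M, that is 0.63 to 2.50 instead of 1.

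**Step 5: ending the exa-cel year at mobilization.** Then m = 0 and M = 1.00 for every k.

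**Text check, needing no assumption.** The therapy window has two end points (conditioning in 9.7.1; HSCT in 9.3.5 and footnote a), and footnote a itself uses one anchor for events and another for therapies. The laboratory baseline has two rules. The 9.7.1 rule turns on the start of treatment, which could mean mobilization, conditioning or Day 0; the same section names the last two as separate points.

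**The case against.** Conditioning is a defensible anchor: one rule for all cohorts, tied to a listed date, and stated alike wherever transfusions and VOCs are counted. Effectiveness is a secondary objective in a study that proposes no prior hypotheses. The proportions free of transfusion or VOC and the event-free time from Day 0 (9.7.4) do not use the baseline year at all. Section 9.9.1 also shows that site burden was limited on purpose. All of this stands, and it is why the anchor itself need not be abandoned.

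Several stronger readings are tempting, and the documents do not support them.

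- A reader might infer that preparatory transfusions inflate the exa-cel baseline several-fold. The protocol mentions no such programme, and 9.3.4 counts only RBCs given to manage the primary disease, with anemia as the stated purpose. That may exclude preparatory transfusions, although the text does not say so. VOC counts carry no similar restriction.
- A reader might infer that distortion is established. It requires k to differ from 1, and the documents give neither k nor m.
- A reader might infer that the allo-HSCT year is free of preparation. Only mobilization, autologous collection and manufacture are shown to be exa-cel-specific; other preparatory care before allo-HSCT is not described.
- A reader might take baseline severity as the planned stratifier. In 9.7 it is an example of a subgroup factor, and the prespecified list in 9.9.2 (age group, genotype, country) does not include it.

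What the objection does not answer is that the interval cannot be separated afterwards from the data listed, so the size of the problem could not be checked. Forms not shown may collect more, but the protocol does not say so.

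**Conclusion.** The concern holds as a risk of baselines that are not comparable. It is not a demonstrated bias, and the transfusion and VOC anchor is not self-contradictory. The exa-cel baseline year normally includes preparation time that the allo-HSCT year does not have, and the listed variables give no means of removing it.

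Under assumed values of 2 to 9 months and a rate ratio of 0.5 to 3, the recorded baseline is 0.63 to 2.50 times the true one; with unchanged rates it is 1.00. The exposure is greatest for absolute change, severity subgroups and the between-cohort baseline comparison, and small for relative reduction when post-transplant events are rare.

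The therapy-window contradiction and the two laboratory rules are errors of wording that rest on no assumption. They do not by themselves show that the event rates are biased.

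**What to change.** - Add the mobilization start date (Exa-cel Cohorts) to 9.3.5, Table 2 and the study-specific forms, which 9.3 says are still being developed.
- For those cohorts, collect transfusion and, in SCD, severe VOC counts for the 12 months before mobilization and, separately, for mobilization to conditioning.
- Keep conditioning as the common anchor if preferred. In that case its own 12-month count must stay on the form, because the two new totals do not add up to it.
- Report the pre-post and baseline-severity results with the pre-mobilization year, at least as a prespecified sensitivity analysis, and show the preparation interval separately.
- State in 9.3.4 whether transfusions given in preparation for cell collection count as events.
- Reconcile the therapy window across 9.3.5, 9.7.1 and Table 2 footnote a, and give one laboratory-baseline anchor in 9.7.1 and Table 2 footnote b.

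Cost: for each exa-cel patient, one date and one further count per event type, or two if the conditioning-anchored count is also kept. Recall reaches slightly further back. The rest is wording. After the forms are final and baseline data have been entered, the same change would mean going back to sites.
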